The inflammatory skin disorder AD is characterized by epidermal barrier dysfunction and active AD lesions are accompanied by underlying immune activation.^{1,2,3} Skin lesions have shown increased infiltration by T cells, dendritic cells (DCs), and eosinophils; increased production of cytokines and chemokines; and reactive epidermal hyperplasia, in which epidermal differentiation products (ie, filaggrin and loricrin) are highly suppressed.^{4,5,6} Although AD has been classified as a Th2-dominated disease, other T-cell subsets (eg, Th22, Th17, and Th1 cells) might also contribute to pathogenesis.^{2,3} Key cytokines implicated in the pathophysiology of AD include IL-4, IL-5, IL-13, IL-31, and IFN- γ . These cytokines require JAK1 for signal transduction suggesting that selective JAK1 inhibitors, which modulate the activity of these cytokines, represent a compelling approach to the treatment of inflammatory skin diseases such as AD.⁷

Data from a Phase 2b proof of concept (POC) study (B7451006) that evaluated participants with moderate-to-severe AD showed positive efficacy with the JAK1 inhibitor abrocitinib, as well as an acceptable safety profile, sufficient to support further clinical development in a larger Phase 3 program. Abrocitinib is an orally bioavailable small molecule that selectively inhibits JAK1 by blocking the adenosine triphosphate (ATP) binding site. Abrocitinib has a high degree of selectivity in vitro against other kinases: 28-fold selectivity over JAK2, >340-fold over JAK3 and 43-fold over TYK2, as well as a good selectivity profile over the broader range of human kinases.

Abrocitinib Involvement in Hematopoiesis

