The double-blind treatment period will last from Baseline/Day 1 to Week 12. For all participants, one 4.5 mm skin biopsy (punch biopsy) will be collected from each target treatment area at the specified time points. Lesional skin biopsies will be collected at Baseline/Day 1 (Week 0), Day 29 (Week 4), and Day 85 (Week 12), with an optional lesional skin biopsy collection at Day 15 (Week 2). A non-lesional skin biopsy will be collected at Baseline/Day 1 (Week 0), with an optional non-lesional skin biopsy collection at Day 85 (Week 12). **CCI**

Biopsy samples will be used to perform gene expression by quantitative reverse transcriptase polymerase chain reaction (qRT-PCR), including Taqman Low Density Array (TLDA) PCR, for 48 genes including 2 housekeeping genes (18S and RPLP0), as well as single gene PCR for a few genes that are below detection level on TLDA (see [Table 1](#)). **CC1**

Immunohistochemistry (IHC) analysis will be performed for cellular infiltrates, Keratin 16 (K16) staining, and hematoxylin and eosin (H&E) staining.

Many of the genes to be analyzed in this study are considered key biomarkers associated with AD pathways. For this study, the following biomarkers were selected for the primary endpoint: general inflammation (MMP12), hyperplasia (K16), Th2 immune response (CCL17, CCL18, CCL26), and Th22 immune response (S100A8, S100A9, S100A12).

CC1

The efficacy outcomes (eg, IGA, EASI, % body surface area [%BSA], and peak pruritus numerical rating scale [PP-NRS]) are collected so that any associations between biomarker changes and these efficacy outcomes may be evaluated. The clinical improvement will be correlated with the suppression of individual immune pathways, cellular infiltrates, and changes in epidermal biomarkers. Differences between groups and changes from baseline will be estimated. Tests of hypotheses for differences between treatment groups will not be performed.

Safety will be assessed by physical exams, standard laboratory testing, and collection of AEs.

Refer to the [Schedule of Activities](#) for a complete list of assessments to be performed during the study.

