While statistical tests of hypotheses will not be performed to compare the fold-change from baseline in the abrocitinib groups versus placebo, the point estimates and 95% CIs for the two abrocitinib dose groups will be assessed in relation to those from the placebo group. A fold-change from baseline observed in the abrocitinib groups alone (and correlated with efficacy) but not in the placebo group is likely due to the mechanism of action of abrocitinib.

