5.1. Hypotheses and Decision Rules

There will be no formal hypothesis testing, but the point estimates and 95% two-sided confidence intervals will be reported for the biomarker endpoints, secondary efficacy CCI [REDACTED] endpoints. No adjustments for multiplicity will be performed. Safety endpoints will be summarized descriptively through appropriate data tabulations, descriptive statistics, categorical summaries, and graphical presentations.

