5.2.1. Analysis of Primary Endpoint

The population for the primary analysis will be all participants in the FAS having valid biomarker data at baseline and Week 12.

The primary endpoints in this study include mean fold-changes for the following biomarkers:

- General inflammation (MMP12);
- Hyperplasia (K16);
- Th2 (CCL17, CCL18, CCL26);
- Th22 (S100A8, S100A9, S100A12).

In each participant, expression levels from RT-PCR will be normalized to the housekeeping gene RPLP0 (validated in other studies) by negatively transforming the Ct values to $-dCt$, obtaining an equivalent to log2 scale expression values (reporting unit: log2 [Expression/RPLP0]). The expression values below detection will be estimated for each gene as the 20% of the minimum of unlogged values across all samples (which is equivalent to subtracting 2.321928 from the $-dCt$ minimum value). The expression levels below detection may provide important information about some markers that significantly change with treatment (eg, the expression may decrease below the level of detection after treatment), therefore this imputation is an important step in the analysis.

RT-PCR expression data in log2 scale will be modeled using a mixed effect model with Treatment, Time Point, and Tissue Type as a fixed effect and a random intercept for each participant. This model will yield unbiased estimates and valid inferences in the presence of a missing data mechanism that is missing at random (MAR).¹ This approach introduces less bias than restricting the analysis for participants with complete observations. Contrasts will be used to estimate the log2 fold-changes for each treatment group. Fold-changes will be computed by obtaining the antilog of log2 fold-changes. Point estimates and 95% confidence intervals (CIs) will be obtained for the fold-change from baseline in the biomarker values for each treatment group based on this model.

Correlation analyses will be performed to assess if the fold-change from baseline in biomarkers correlates with change (from baseline) in the clinical efficacy endpoints such as IGA, EASI, and Peak Pruritus NRS.

Supportive analyses for the primary endpoint will also be performed using the PPAS.

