While statistical tests of hypotheses will not be performed to compare the fold-change from baseline in the PF-04965842 groups versus placebo, the point estimates and 95% CIs for the two PF-04965842 dose groups will be assessed in relation to those from the placebo group. A fold-change from baseline observed in the PF-04965842 groups alone (and correlated with efficacy) but not in the placebo group is likely due to the mechanism of action of PF-04965842.

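### The plan's conditions for crediting a biomarker change to abrocitinib's mechanism can support an effect of treatment, but cannot tell pathway action from healing

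*SAP*

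**What the plan says.** SAP 5.2.1 closes the primary analysis with an interpretive sentence. A fold-change found in the active groups alone "and correlated with efficacy) but not in the placebo group is likely due to the mechanism of action of PF-04965842". Protocol 9.4.1 says the same under the other drug name: "and correlated with efficacy) but not in the placebo group is likely due to the mechanism of action of abrocitinib".

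The SAP gives the purpose of the correlation as: "assess if the fold-change from baseline in biomarkers correlates with change (from baseline) in the clinical efficacy endpoints such as IGA, EASI". The itch score is named there as well. The readable text gives no coefficient, cut-off, choice between pooled and within-arm calculation, or adjustment.

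On the comparison with placebo, SAP 5.2.1 says that "statistical tests of hypotheses will not be performed to compare the fold-change from baseline"; the intervals of the active arms are read against that of placebo. SAP 5.1 adds that "point estimates and 95% two-sided confidence intervals will be reported for the biomarker endpoints" and "No adjustments for multiplicity will be performed". SAP 6.1.1 lists one primary summary, the Week 12 fold-change from baseline.

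Protocol 4.1 states the intended use: "The clinical improvement will be correlated with the suppression of individual immune pathways, cellular infiltrates, and changes in epidermal biomarkers". The same section says that between-group differences will be estimated, but neither Protocol 9.4.1 nor SAP 6.1.1 carries that into the primary analysis.

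**The concern.** The trial exists to investigate mechanism of action. With no hypothesis test planned, this sentence is the only readable link from the primary data to that purpose. It sets three conditions: the marker changes on active drug, it does not change on placebo, and its change correlates with clinical improvement.

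Randomisation lets a difference between arms be read as caused by treatment. It does not show the route. If the drug clears the skin and a marker simply follows lesion severity, all three conditions are expected with no direct action on that marker's pathway. The third condition makes this worse, because it selects markers that move with disease activity. A marker suppressed directly in participants who did not improve would tend to fail it.

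Several features of the plan make this a practical concern:

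- MMP12 is labelled general inflammation and K16 hyperplasia, and the Introduction describes lesions as showing "reactive epidermal hyperplasia, in which epidermal differentiation products" that are suppressed.
- The primary summary is at Week 12, and the same area is biopsied even if it has cleared (Protocol 8.1.2). In the Phase 2b study, IGA and EASI on 200 mg improved until Weeks 4 and 6 (Protocol 2.2.2), so Week 12 is well after clinical response.
- The Week 2 lesional and Week 12 non-lesional biopsies, which could help separate drug action from healing, are optional (Protocol 4.1), and the sentence uses neither.

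**Working it through.** **1. The plan's own figure.** The sample-size section gives about a 92% chance that the within-arm 95% CI half-width is at most 3.2, with n = 17 and SD 5. The half-width is t(0.975, 16) × s/√17, so s must not exceed 3.2 × 4.123/2.120 = 6.224. Then 16 × (6.224/5)² = 24.79, and P(χ² with 16 df ≤ 24.79) = 0.926. The figure reproduces. It concerns precision within one arm and says nothing about attribution.

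**2. Inputs for the attribution check.**

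| Input | Value | Source |
|---|---|---|
| Participants per arm | 17 | Protocol 9.2, SAP 2.2 |
| Mean EASI improvement, 200 mg / 100 mg / placebo | 63.7% / 41.6% / 15.6% | Protocol 2.2.2, illustrative only |
| SD of improvement | 35 points | assumption |
| Marker fall per 100% improvement | 2 to 4 log2 units | assumption |
| Residual SD | 1 to 2 log2 units | assumption |
| Correlated with efficacy | within-arm correlation, p < 0.05, 47 df | assumption |
| Direct drug effect on the marker | none | by construction |

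Protocol 2.2.2 prints 63.7, 41.6 and 15.6 both as percent change in EASI and as EASI-75 rates. Its stated 200 mg difference is 41.8, whereas 63.7 − 15.6 = 48.1. These inputs are therefore illustrative.

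**3. By hand, middle setting (slope 3, residual SD 1.5).**

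- Expected log2 changes: −3 × 0.637 = −1.91, −3 × 0.416 = −1.25, −3 × 0.156 = −0.47.
- Total SD: √[(3 × 0.35)² + 1.5²] = √3.3525 = 1.83.
- CI half-width: 2.120 × 1.83/4.123 = 0.94.
- Expected intervals: both active arms exclude zero (−1.91 ± 0.94 and −1.25 ± 0.94); placebo includes it (−0.47 ± 0.94).
- Expected within-arm correlation: 1.05/1.83 = 0.57 in size. The critical value at 47 df is 2.012/√(47 + 2.012²) = 0.28.

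All three conditions are met on average by a marker on which the drug has no direct action.

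In the weakest setting (slope 2, residual SD 2) the expected changes are −1.27, −0.83 and −0.31. The SD is √(0.49 + 4) = 2.12 and the half-width 2.120 × 2.12/4.123 = 1.09. The 200 mg arm still passes on average and the 100 mg arm does not. This is why requiring both arms lowers the bottom of the range.

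**4. Simulation over slopes 2, 3, 4 and residual SDs 1, 1.5, 2.** A purely downstream marker met all conditions in about 14% to 69% of trials if both active arms must change, and 47% to 83% if one must. Separate runs on the same grid gave 12% to 70% and 44% to 83%, so the ends are good to about three points.

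**5. What the correlation condition selects.** A second simulation required both arms to change, with slope 3, healing SD 0.3 to 0.4, residual SD 1 to 2, and placebo improvement 0 or 15.6%. With a within-arm correlation, a downstream marker passed in 40% to 90% of trials. A marker moved directly by the drug, with the same arm means and total SD but no within-arm link to healing, passed in 2% to 4%. With a pooled correlation the ranges were 42% to 90% and 6% to 65%; arm differences alone can then create the association. A marker affected by neither passed in about 0%.

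**6. Would adjusting for EASI rescue the mechanism claim?** If EASI were an error-free measure of healing at the biopsy site, a downstream marker would keep a nominally significant 200 mg versus placebo difference in about 4% to 6% of trials. EASI is a whole-body score (Protocol 8.1.7), while biopsies come from one target area (8.1.2). With an error SD of 20 points the figure is 7% to 16%. For a true mediator (drug changes marker, marker changes skin), EASI is a consequence of the marker, and adjustment can remove the effect being sought. Such a marker kept its difference in only 6% to 22% of trials under one set of assumptions, and lost it in 10% to 85% under another. The size depends heavily on the assumed errors, but the adjustment can err in both directions.

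**The case against.** The text is hedged, nothing is tested, and no readable decision depends on it. The stated primary objective is to assess effects on biomarkers, not to issue a verdict on mechanism. Six of the eight markers are labelled Th2 or Th22 immune response, and the Introduction says that key AD cytokines need JAK1, so treating every marker as a mere severity tracker is an assumption. Parts of the biomarker analysis are redacted, and the SAP version history moves RNA analyses to a supplementary biomarker SAP, where a separating analysis may exist.

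All of this stands as a limit on size. It does not repair the step. With no test, the interpretive sentence carries the conclusion, and it refers to no further analysis. If mechanism was meant only as drug effect, saying so costs nothing.

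A reader might go further and infer that any treatment that clears skin would earn the mechanism statement, or that a false one is almost certain. Counting at least one of eight markers, with one active arm sufficient, does give 91% to 99.6% in simulation. The documents do not support that reading. The sentence speaks of groups in the plural, sets no p-value cut-off, and does not treat one marker in eight as enough. The simulation also assumes that all eight markers are driven only by healing.

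**Conclusion.** The concern holds as a flaw of inference. The three conditions can support an effect of treatment; they do not separate direct pathway action from a marker that falls because the skin healed, and the third favours markers of disease activity. For a purely downstream marker, passing is probable over much of the range examined but not certain. It presupposes a treatment that clears skin more than placebo. The percentages rest on assumed SDs, slopes and a p < 0.05 correlation, and on Phase 2b figures that the protocol reports inconsistently; the logical point does not depend on them.

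It should not be inferred that the fold-change estimates or their intervals are wrong. They are not affected.

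**What to change.** In SAP 5.2.1 and Protocol 9.4.1:

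1. Base the conclusion on the estimated active-minus-placebo difference in log2 fold-change with its 95% CI, at Week 12 with Week 4 in support, instead of reading within-arm intervals side by side. This is estimation, not a test, and Protocol 4.1 already promises between-group differences. It is a contrast from the same mixed model, provided the model carries the treatment-by-time term that its per-arm changes already need.
2. Replace the words crediting the change to the drug's mechanism with: *is consistent with an effect of treatment with*.
3. Add: *Correlation with efficacy describes how the marker tracks disease activity and is not by itself evidence of mechanism.*

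The wording change is needed as well as the contrast. A downstream marker can show a real difference from placebo: with a 200 mg versus placebo contrast in place of the first two conditions, it still passed in 16% to 89% of simulated trials.

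Do not reserve mechanism wording for markers whose difference persists after adjustment for EASI, because that adjustment can remove the effect of true mediators. If an EASI-adjusted estimate is shown, label it descriptive only.

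Cost: a few sentences in two documents and one contrast per marker, dose and visit, from required biopsies. No new samples are needed. The downside is a less favourable headline claim.

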5.2.2. Analysis of Other Biomarker Endpoints

In addition to the key biomarkers considered as primary endpoints, the other biomarkers endpoints in this study include (but may not be limited to) the following:

Parameters studied using IHC will include epidermal thickness (performed on H&E sections), Ki 67+ cells, Keratin 16 (K16), CCI [REDACTED]
[REDACTED].

CCI

CCI

CCI

CCI

Gene expression by TLDA RT-PCR will include the levels of the following established cytokines associated with AD: CCI

CCI S100A7, S100A8, S100A9, S100A12,
CCI CCL18,
CCI CCL26, CCI 18S and

RPLP0 as control genes.

CCI

The mixed-effect model approach chosen for the analysis of RT-PCR and IHC data has the advantage that estimation of the parameters in the models is unbiased and valid inferences are possible in the presence of a missing data mechanism that is MAR. This approach introduces less bias than restricting the analysis for participants with complete observations.

5.2.3. Analyses of Other Endpoints

The responses based on IGA, EASI (eg, EASI-75), and severity scale of the Peak Pruritus NRS will be summarized descriptively by visit and treatment. The difference of the improvement from baseline between each PF-04965842 dose and placebo will also be derived.

If a participant withdraws from the study, then this participant will be considered a non-responder after withdrawal for any binary valued clinical efficacy endpoint.

CCI

CCI

5.3. Methods to Manage Missing Data

In general, for analyses using descriptive statistics, missing values will not be explicitly imputed. In addition, for safety endpoints, missing values will not be imputed.

For the responses based on IGA, EASI (eg, EASI-75), and severity scale of the Peak Pruritus NRS, if a participant withdraws from the study, then this participant will be considered a non-responder after withdrawal for any binary valued clinical efficacy endpoint.

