7. DISCONTINUATION OF STUDY INTERVENTION AND PARTICIPANT DISCONTINUATION/WITHDRAWAL

7.1. Discontinuation of Study Intervention

In certain instances, it may be necessary for a participant to permanently discontinue study intervention (ie, study treatment). If study intervention is permanently discontinued, the participant will remain in the study to be evaluated for EOT assessments (per [Schedule of Activities](#)).

Note that discontinuation of study treatment does not represent withdrawal from the study. Refer to [Appendix 10](#) for discontinuation criteria.

See the [Schedule of Activities](#) for data to be collected at the time of intervention discontinuation and follow-up and for any further evaluations that need to be completed.

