9.4.2.1. Analysis of Other Endpoints

The responses based on IGA, EASI (eg, EASI-75), and severity scale of the Peak Pruritus NRS will be summarized descriptively by visit and treatment. The difference of the improvement from baseline between each abrocitinib dose and placebo will also be derived.

If a participant withdraws from the study, then this participant will be considered a non-responder after withdrawal for any binary valued clinical efficacy endpoint.

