2.2. Study Design

This is a randomized, double-blind, placebo-controlled, parallel-group, Phase 2a study to investigate the mechanism of action of PF-04965842 by correlating efficacy outcomes with changes from baseline in key skin and blood biomarkers in adult participants ≥ 18 years of age with moderate-to-severe AD. Participants will be screened within 28 days prior to the first dose of study intervention to confirm study eligibility. A total of approximately 51 participants will be randomized in a 1:1:1 ratio to receive PF-04965842 200 mg QD, PF-04965842 100 mg QD, or matching placebo QD for 12 weeks. A study design schematic is presented in Figure 1.

Figure 1 Study Design Schematic

At the end of the 12-week study treatment, qualified participants will have the option to enter the long-term extension (LTE) Study B7451015. Participants discontinuing early from this study will undergo a 4-week off-treatment follow-up period.

Eligible participants will be randomized into 3 intervention groups in the study:

Group 1 (N=17): PF-04965842 200 mg QD taken orally for 12 weeks.

Group 2 (N=17): PF-04965842 100 mg QD taken orally for 12 weeks.

Group 3 (N=17): placebo QD taken orally for 12 weeks.

The total duration of participation in the study is up to 20 weeks, including up to 4 weeks for screening, 12 weeks study intervention, and a follow-up period of 4 weeks after study intervention (for those participants who do not enter the LTE study).

A full schedule of activities for the study is provided in Appendix 7.

Sample Size Determination

The sample size of this study is based on the objective to evaluate changes in key AD biomarkers in skin lesions, including biomarkers for general inflammation (MMP12),

hyperplasia (K16), Th2 (CCL17, CCL18, CCL26), and Th22 (S100A8, S100A9, S100A12) with PF 04965842 200 mg QD, PF 04965842 100 mg QD, and placebo.

A total sample of approximately 51 participants, with 17 participants randomized to PF-04965842 200 mg QD, 17 participants randomized to PF-04965842 100 mg QD, 17 participants randomized to matching placebo (1:1:1 randomization) is planned.

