5.1.1. Estimands

The primary objective of this study is to assess the effects of PF-04965842 on lesional and non-lesional skin biomarkers of adult participants with moderate-to-severe AD. A hypothetical estimand will be used for estimation. The following estimand attributes will be considered:

- Population: Participants with moderate-to-severe AD as defined by the inclusion criteria and with a valid baseline and Week 12 assessment;

- Variable: Fold-change from baseline in the biomarkers for general inflammation (MMP12), hyperplasia (K16), Th2 immune response (CCL17, CCL18, CCL26), and Th22 immune response (S100A8, S100A9, S100A12);
- Intercurrent event: All data collected will be utilized;
- Population-level summary: Mean fold-change from baseline within each treatment group.

Some secondary objectives require analyses of binary endpoints for which, a composite estimand with the following attributes will be considered:

- Population: Participants with moderate-to-severe AD as defined by the inclusion criteria and with a valid baseline;
- Variable: Binary outcome measures such as responder-based endpoints. Participants who discontinue from the study treatment for any reason are defined as non-responders after that point;
- Intercurrent event: The intercurrent event is captured through the variable definition;
- Population-level summary: Proportion of participants who are responders in each treatment group and differences in proportions of responders between each active dose and placebo.

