6.3. Efficacy Endpoints

6.3.1. NRS4 for Severity Response

- Summary: Proportion of subjects with NRS4 for severity response at Weeks 4, 8 and 12;
- Population: Subjects from the FAS with a baseline NRS score for severity ≥ 4 ;
- Statistical Method: Descriptive (n, %), 95% CI and difference from placebo. Visit windows will be used as described in Appendix 2;
- Missing Data: Missing data arising due to subject dropout are considered “non-response”.

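### For the descriptive responder endpoints the SAP's non-response rules conflict, its day windows can admit off-treatment Visit 11 data to Week 12, and its Appendix 1 does not match the body

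*SAP*

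**What the plan says.** **Non-response.** The composite estimand for binary endpoints in SAP 5.1.1 reads: "Participants who discontinue from the study treatment for any reason are defined as non-responders after that point". Its population summary includes "differences in proportions of responders between each active dose and placebo". SAP 5.2.3 reads: "If a participant withdraws from the study, then this participant will be considered a non-responder after withdrawal". SAP 5.3 repeats, for the IGA, EASI and Peak Pruritus responses, that "if a participant withdraws from the study, then this participant will be considered a non-responder after withdrawal for any binary valued clinical efficacy endpoint", and protocol 9.4.2.1 carries the same rule. The missing-data bullets in SAP 6.3.1 to 6.3.3 use another term: "Missing data arising due to subject dropout are considered" non-response.

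**The two events.** Protocol 7.1 separates them: "Note that discontinuation of study treatment does not represent withdrawal from the study". Protocol 7.2.1 keeps people who ask to stop treatment under follow-up. SAP 2.2 blurs the terms: "Participants discontinuing early from this study will undergo a 4-week off-treatment follow-up period".

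**Visits.** The schedules place Visit 11 four weeks after the last dose in case of early termination, with IGA and EASI marked there. SAP Section 6 applies the Appendix 2 windows to all efficacy analyses and sends Week 16 data to listings unless noted otherwise. Appendix 2 defines Week 12 as Days 72 to 99 and Week 16 as Day 100 onward.

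**Appendix 1.** SAP Section 6 cites this table as the summary of the clinical efficacy analyses. It marks Week 12 IGA and EASI-75 response as co-primary in the FAS, with CMH as the method.

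**The concern.** A participant who stops the drug but stays in the study meets the 5.1.1 condition for non-response but not the one in 5.2.3, 5.3 or protocol 9.4.2.1. If an IGA or EASI value then falls in an analysis window, nothing is missing, so the 6.3 bullets do not apply either. Depending on the section programmed from, that person is a non-responder or is scored on a value taken about four weeks off treatment.

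Appendix 1 raises a separate problem. A table that calls two clinical endpoints co-primary, names a method usually associated with a test, and gives NRS4 different visits and imputation leaves open which analysis is the planned one. If these choices are settled after unblinding, they may be made with the results in view.

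**Working it through.** **1. Triggers side by side.** Take a participant with a last dose on Day 57 who stays in the study and meets EASI-75 at a visit on Day 85.

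| Section | Trigger | Week 12 result |
|---|---|---|
| SAP 5.1.1 | stopping study treatment | non-responder |
| SAP 5.2.3, 5.3; protocol 9.4.2.1 | withdrawing from the study | rule not met; observed responder if the visit is mapped to Week 12 |
| SAP 6.3.3 | missing because of dropout | value not missing; observed responder if mapped |

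**2. Where Visit 11 lands.** Inputs are the timing of Visit 11 (last-dose day D plus 28) and the Appendix 2 day windows. Solving lower limit ≤ D + 28 ≤ upper limit, with D at least 1:

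| Analysis window | Last-dose days that place Visit 11 there | D that hits the target day |
|---|---|---|
| Week 4, Days 23–36 | 1–8 | 1 (Day 29) |
| Week 8, Days 51–71 | 23–43 | 29 (Day 57) |
| Week 12, Days 72–99 | 44–71 (28 days) | 57 (Day 85) |

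For D of 72 or more, the visit is on Day 100 or later and is only listed. These are nominal days; the ±3-day tolerance for Visit 11 shifts the edges by up to 3 days. At D = 57 the follow-up falls exactly on the Week 12 target, so the closest-to-target rule would keep it. By Appendix 2's own definition a visit before Day 100 is not Week 16, so the listings-only sentence does not clearly exclude it. I show this for IGA and EASI only, because the Peak Pruritus row of the schedule cannot be read reliably in the text available.

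**3. Size.** With the planned 17 per arm, one participant scored differently moves the arm's rate, and its difference from placebo, by 1/17 = 5.9 points. For scale, assume the Phase 2b IGA rates in protocol 2.2.2 (44.5%, 27.8% and 6.3% for 200 mg, 100 mg and placebo):

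- 100 mg minus placebo: 27.8 − 6.3 = 21.5, and 5.9/21.5 = 27%.
- 200 mg minus placebo: 44.5 − 6.3 = 38.2, and 5.9/38.2 = 15%.
- Approximate 95% CI half-width for one arm at 44.5%: 1.96 × √(0.445 × 0.555/17) = 23.6 points.
- For the difference 44.5% versus 6.3%: 1.96 × √(0.445 × 0.555/17 + 0.063 × 0.937/17) = 26.3 points.

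**4. Appendix 1 against the body.**

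| Item | Appendix 1 | Body of the SAP |
|---|---|---|
| Week 12 IGA, EASI-75 | co-primary | secondary efficacy (3.3); only biomarkers primary (3.1, 6.1) |
| Method for responders | CMH | descriptive (6.3.1–6.3.3); no formal testing (5.1) |
| NRS4 visits | Weeks 2, 4, 8, 12 | Weeks 4, 8, 12 (6.3.1) |
| NRS4 missing data | NR+MI rows and an NR row | non-response (6.3.1) |
| EASI-100 | listed | absent from 6.3.3 |
| Time to NRS4 | Kaplan-Meier | no counterpart in the readable 6.3 |
| %BSA | MMRM | labelled descriptive (6.3.4) |

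**5. Design figure.** The only stated one is the roughly 92% chance of a CI half-width of at most 3.2 with 17 per arm and SD 5. Using the t quantile on 16 degrees of freedom and a chi-square distribution for the sample variance, I get 92.6%. It concerns biomarker fold-change and does not depend on anything above.

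**The case against.** The strongest reply is that the sections fit together: 5.1.1 defines the outcome and captures the intercurrent event, while 5.3 handles data absent after withdrawal. Nothing says that a treatment discontinuer is scored on observed data. Visit 11 is labelled Week 16 in the schedule, Section 6 keeps Week 16 in listings, and the endpoints are descriptive with no decision rule.

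Much of this is fair. If 5.1.1 is applied throughout, or the visit label governs, the Visit 11 route closes. But 5.2.3, 5.3 and 6.3 do not refer back to 5.1.1, and the SAP does not say whether label or study day governs.

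Several stronger readings should be resisted:

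- A reader might take *dropout* as a third rule. It sits in missing-data bullets and can mean study withdrawal, so it is an ambiguity.
- A reader might infer from 6.6, which also says co-primary, that IGA and EASI-75 were meant to be primary. That section points to the biomarker model of 5.2.1.
- A reader might think CIs and differences for IGA and EASI are unplanned because 6.3.2 and 6.3.3 list only n and %. Sections 5.1, 5.2.3 and 6 already promise them.
- The PPAS rows are not barred by 4.2, which names the primary endpoint without saying only. CMH can also supply an estimate without a test.
- A reader might want anyone who stops before Day 82, when the Week 12 visit window opens, scored as a Week 12 non-responder. That could reclassify a completer seen on Day 80 or 81 whose value lies in the SAP's window.

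Redacted text, including Appendix 3 and part of 5.2.3, may explain some NRS entries. It cannot remove the conflicts in the readable text.

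**Conclusion.** The conflict is real and lies in the current SAP. Treatment discontinuation and study withdrawal are both given as the non-response trigger, and the protocol says they are different events. By study day, off-treatment IGA or EASI after a last dose on Days 44 to 71 enters Week 12, contrary to the evident intent that follow-up data are only listed. Appendix 1 contradicts the body on endpoint status and on NRS4, and does not match it on EASI-100, time to NRS4 and %BSA.

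The effect is 5.9 points per participant scored differently, assuming 17 per arm. That is not negligible beside the assumed Phase 2b differences but small beside a CI half-width of about 24 points. The documents give no discontinuation rate. The shift is zero if nobody stops early, or if no early stopper meets the response definition at the visit concerned.

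A reader might infer that the trial's main result is at risk. The documents do not support that: the responder endpoints are not primary, no hypothesis is tested, and the biomarker analysis and sample size do not use these rules.

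**What to change.** Before unblinding, amend the SAP:

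- **(a) One trigger.** State in 5.2.3, 5.3 and 6.3.1 to 6.3.3 that a participant is a non-responder at all visits after permanent early treatment discontinuation or study withdrawal, whichever is first. Replace *dropout* with this wording. Note that it modifies protocol 9.4.2.1; SAP Section 2 calls for a protocol amendment only for major changes to the primary endpoint or its analysis.
- **(b) Visit mapping.** Add to Appendix 2 that post-treatment follow-up (Visit 11) assessments are never mapped to Weeks 2 to 12 for efficacy. State that an early-termination visit is scored under the 5.1.1 rule, while participants who complete planned treatment keep their observed value in the existing window. Add no Day-82 cut-off.
- **(c) Labels.** Delete the co-primary column in Appendix 1, and in 6.6 refer to the primary biomarker endpoints.
- **(d) Appendix 1.** Make it agree with 6.3 on visits, method and imputation, including EASI-100, time to NRS4 and %BSA. Label CMH as estimation without a test and the PPAS rows as supportive. State which NRS4 imputation leads; either choice is defensible if made in advance.

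The cost is SAP wording and some table alignment, with no new data. Response rates may be slightly lower because treatment discontinuers count as non-responders.
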